CPRS will also be used to complete a review following the second visit with subjects to collect information on appointment no shows, early termination of services, results of Urinary Drug Screen (UDS) and Breathalyzer collections, and results of the Beck Depression Inventory and Quality of Life Inventory administered during the SATP intake. 90 days following this chart review, a second chart review will occur to collect the same information, if available, for the post-treatment time period, along with information about whether they have re-entered treatment.

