**Visit One:**

The following self-report measures (questionnaires) will be administered with paper-and-pencil:

*Brief Addiction Monitor (BAM)* – The BAM is a 17-item self-report questionnaire that assesses the recent occurrence and frequency of various substances, including marijuana, cocaine, stimulants, and opiates. It additionally has items for the rater to respond to recent health (excellent, very good, good, fair, poor), and recent engagement in risky situations or treatment. Lastly, it has several items asking about symptoms of substance use disorder, such as cravings and difficulties related to substance use (Cacciola et al., 2013). We hypothesize subjects with more reported substance use and less engagement in treatment resources will have poorer treatment adherence. This measure will take approximately 10 minutes to complete.

*Barratt Impulsiveness Scale (BIS-11)* - The BIS-11 is a reliable and valid self-report measure of attentional, motor, and non-planning impulsivity composed of 30 items rated on a 4 point Likert scale from rarely/never to almost always/always (Patton, Stanford, & Barratt, 1995). We hypothesize subjects with higher impulsivity will be more likely to have poorer treatment adherence. This measure will take approximately 10 minutes to complete.

*PTSD Checklist 5* - This is a VA-distributed measure of 20 PTSD-related symptoms (each scored from 0-4) that align with DSM-5 PTSD criteria. It is administered in addition to the SCID itself in order to provide a continuous variable of PTSD symptom severity (Bovin et al., 2016). This measure is being used to account for potential confounding symptomology that may lead to treatment adherence issues. This measure will take approximately 10 minutes to complete.

*Beck Anxiety Inventory* - This is a tally of the subject's self-reported experience of 21 different anxiety-related symptoms in the past week-including the day of testing, where each item is rated on a scale from 0-3 (A. T. Beck, Epstein, Brown, & Steer, 1988). This measure is being used to

account for potential confounding symptomology that may lead to treatment adherence issues. This measure will take approximately 10 minutes to complete.

Visit Two:

The following self-report measures (questionnaires) will be administered with paper-and-pencil:

*Barratt Impulsiveness Scale (BIS-11)* – See above for description

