#### Data Analysis

The analytic plan includes conducting an independent-group t-test of each of the following continuous dependent variables, or chi-square for categorical dependent variables: 1)

proportion drug-free urines; 2) retention in program (Chi-Square); 3) Quality of life score on the QOLI; 4) Delay discounting constant k; 5) Stop signal reaction time (SSRT) on the stop-signal task; 7) Reaction time in the Emotional Go-NoGo task, 8) errors in the DKEFS Tower Test.

A repeated-measures design will be used to examine the within-subjects effects of the treatments on state depression and quality of life, as well as for a group X treatment interaction effect. Although we do not expect an intervention of this time scale of to alter trait impulsivity, we will also analyze within-subject changes in BIS11 scores as an exploratory analysis. Lastly, a between-group design comparing the MFP group vs. TAU group for substance use primary outcomes of symptomology and neurobehavioral measures for problem solving and impulsivity. Individual differences in PTSD and anxiety measures and other symptomatology will be included as covariates to account for confounding factors in the analyses.

c. Facilities and Resources

The consent procedures and behavioral testing of this protocol will take place in the new second-floor Mental Health services facility at RICVAMC. Written informed consent procedures and clinical interviewing will take place in private interview rooms of this new second-floor RICVAMC wing. Questionnaires and laboratory behavioral tasks will be administered at dedicated research task workstations installed in testing rooms.

d. Staff Qualifications

*[name].* will be the Principal Investigator of this protocol. [name] has a 5/8 VA appointment and a joint (faculty) appointment as Associate Professor of Psychiatry at Virginia Commonwealth University. He has extensive experience in the laboratory testing of impulse control and decision-making in addicted inpatients, outpatients, and at-risk human subjects. He is also known for his successful design and execution of protocols to examine the neurocircuitry of motivation and self-control in addicted and adolescent at-risk populations. He has over 50 peer-reviewed publications and book chapters, 48 of which are available in PUBMED.

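### The listed t-tests and chi-square cannot carry the covariates that the same section promises, and quality of life is analysed twice with no leading result

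*Protocol*

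**What the plan says.** The Data Analysis section opens: "The analytic plan includes conducting an independent-group t-test of each of the following continuous dependent variables, or chi-square for categorical dependent variables". Seven items follow, numbered 1 to 5, 7 and 8. The first is the proportion of drug-free urines. Next come "2) retention in program (Chi-Square); 3) Quality of life score on the QOLI", then the discounting constant, stop-signal reaction time, Go-NoGo reaction time and Tower Test errors. The sentence does not say which groups are compared.

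The second paragraph adds: "A repeated-measures design will be used to examine the within-subjects effects of the treatments on state depression and quality of life", and continues "as well as for a group X treatment interaction effect". BIS-11 change is an exploratory within-subject analysis. A further comparison follows: "Lastly, a between-group design comparing the MFP group vs. TAU group for substance use primary outcomes of symptomology and neurobehavioral measures". The covariate sentence closes the paragraph: "Individual differences in PTSD and anxiety measures and other symptomatology will be included as covariates to account for confounding factors in the analyses".

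Two other places bear on this. Under Visit One, the PCL-5 and the Beck Anxiety Inventory (BAI) share one justification: "This measure is being used to account for potential confounding symptomology that may lead to treatment adherence issues". Under Procedures, the chart review collects "results of the Beck Depression Inventory and Quality of Life Inventory administered during the SATP intake", so pre-treatment values of both instruments should be on file.

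**The concern.** The covariate promise has no stated limit, yet the tests named for the listed outcomes are unadjusted. Retention shows this most plainly. PCL-5 and BAI are collected because they may confound adherence, but the only test named for retention is a chi-square, which cannot use them.

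The QOLI is named in two analyses. If both compare MFP with TAU, they address the same question, can give different answers, and leave the choice open until the data are seen.

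The interaction is also miswritten. By the project timeline each Veteran receives either MFP or TAU, so treatment is the group. In a repeated-measures analysis the meaningful term is group x time.

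**Working it through.** **Reading the text.** The protocol gives no alpha, power, effect size or SD, so there is no figure to reproduce. The covariate sentence can be read in three ways:

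- *It covers all the analyses.* The listed tests cannot carry what is promised.
- *It covers only the second paragraph.* The t-tests are not contradicted, but the QOLI has two analyses and no leading one. If the MFP v TAU sentence is a separate analysis and the list also compares MFP with TAU, the neurobehavioral measures are tested twice as well.
- *The MFP v TAU sentence restates the list.* The neurobehavioral measures are then tested once, but the covariates attach to the listed tests and the first problem returns.

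Each reading leaves something to settle.

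**Inputs for the size.** From the protocol: about 35 Veterans (Study Design). Assumed: a 17 v 18 split, complete data, MFP v TAU as the grouping, item 3 tested on the post-treatment score, a true difference d = 0.8 SD, two-sided 5%, and intake-post correlation r of 0.3 to 0.7.

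**Formulas.** Relative to the post-score variance, the comparison has variance factor 1 for the t-test, 2(1 − r) for change (the same as group x time with two time points), and 1 − r² for a linear model on intake (ANCOVA). The effective effect size is 0.8/√factor:

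- r = 0.3: change 0.8/√1.40 = 0.68; ANCOVA 0.8/√0.91 = 0.84
- r = 0.5: change 0.8/√1.00 = 0.80; ANCOVA 0.8/√0.75 = 0.92
- r = 0.7: change 0.8/√0.60 = 1.03; ANCOVA 0.8/√0.51 = 1.12

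**Simulated power for QOLI** (100,000 replicates per cell):

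| r | t-test | group x time | ANCOVA, intake only | ANCOVA, intake + PCL-5 + BAI explaining nothing |
|---|---|---|---|---|
| 0.3 | 63.3% | 49.3% | 65.9% | 62.9% |
| 0.5 | 63.4% | 63.4% | 74.1% | 71.3% |
| 0.7 | 63.3% | 84.2% | 88.6% | 86.4% |

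**Two QOLI tests, no true effect.** At least one is significant in 9.2% of trials at r = 0.5 and 9.4% at r = 0.7. Two independent tests would give 1 − 0.95² = 9.75%.

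**Other continuous outcomes** (no intake value; PCL-5 and BAI as covariates). Against about 63% unadjusted, power is 60.4% if the covariates explain nothing, 64.8% at R² = 0.1 and 70.1% at R² = 0.2. If such an outcome is tested both with and without adjustment, at least one test is significant under no effect in 6.0% to 7.4% of trials.

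**Retention.** With 5 to 15 drop-outs (assumed), a model with group and two covariates has 5/3 = 1.7 to 15/3 = 5.0 events per parameter. That is too few for an adjusted model to lead.

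**The case against.** The strongest reply is that the covariate sentence closes the second paragraph and belongs only there, so nothing conflicts with the t-tests. The text allows that reading, and the conflict is therefore conditional. The two QOLI analyses remain.

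A second reply is that the list may not compare MFP with TAU at all. Aim 1 concerns treatment success and adherence, MFP v TAU is only the exploratory aim, and the hypotheses given for QOLI, the Tower Test, delay discounting and the stop-signal task concern adherence. On that reading the two QOLI analyses answer different questions. Against it, items 1 and 2 of the list are themselves treatment-success and adherence outcomes, which fits poorly with grouping by adherence. The grouping is unresolved, and the QOLI figures hold only for MFP v TAU.

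A third reply is that model detail belongs in a statistical analysis plan. That is fair for the exact covariate list. It does not cover a protocol that names unadjusted tests and promises adjustment in one section.

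A reader might infer more than the documents support:

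- *That the neurobehavioral measures are certainly tested twice.* This depends on whether the MFP v TAU sentence is a separate analysis or restates the list.
- *That disagreement between the two QOLI tests is an error rate.* At d = 0.8 they disagree in about 32% to 34% of simulated trials, but this is largely two moderately powered tests differing when an effect exists.
- *That the fully adjusted model is always more powerful.* At r = 0.3 it has 62.9% against 63.3% for the t-test.

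**Conclusion.** The point holds in a limited form. The section either promises covariates that its named tests cannot use or, on the narrower reading, gives QOLI two analyses without a leading one. The interaction term needs correcting on either reading.

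Under the stated assumptions, the false-positive rate for QOLI is about 9% if either test may count. At correlations of 0.5 to 0.7 the fully adjusted model has about 71% to 86% power, 8 to 2 points above group x time and well above the t-test's 63%. At 0.3 it gains nothing over the t-test.

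QOLI is not labelled primary and no stated number in the protocol is wrong. This is a specification fault worth correcting before analysis; it does not undermine the study.

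**What to change.** In Data Analysis:

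1. State the grouping factor of the test list. If it is MFP v TAU, merge the separate MFP v TAU sentence into the list so that each outcome has one leading test. If it is another grouping, say which question each analysis answers.
2. Replace the t-tests with a linear model containing group, Visit 1 PCL-5 and Visit 1 BAI.
3. For QOLI and BDI-II, add the intake value and make this the leading between-group analysis. Keep repeated measures as supportive for both, with the interaction written as group x time.
4. Leave BIS-11 as the planned exploratory within-subject analysis.
5. Use only covariates measured before treatment. Name the measures meant by other symptomatology, or delete the phrase. As it stands it could take in the Visit 2 BDI-II, although depression is itself an outcome.
6. Keep the chi-square for retention and state that it is unadjusted.

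The cost is wording and a little more analysis; no new data are needed. The downside is about 3 points of power if PCL-5 and BAI explain nothing (63% to 60% for outcomes without an intake value), and a leading retention test that remains unadjusted.

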**1. Purpose and Objectives:**

This protocol does not include any administration of medication or other interventions. This protocol will record cognitive performance and decision-making behavior in Veterans who seek mental health services in the substance use disorder intensive outpatient program (IOP). The goal is to identify the neurobehavioral effects of a structured, brief cognitive-based psychotherapy currently being conducted in the IOP along with other supportive, unstructured, treatments. The benefit of this study will be to obtain a better understanding of neurobehavioral changes occurring from evidence-informed treatments.

Aim 1: To determine if measurable neurobehavioral function in the domains of problem solving, decision making, and motoric impulsivity is predictive of treatment success and adherence outcomes (e.g. Urinary Drug Screen/Breathalyzer Analysis results, appointment no shows, early drop out, recidivism).

Exploratory Aim: To determine if there are between group differences in neurobehavioral function as a result of treatment modality being received as standard of care in the substance use outpatient setting.

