**2. Background, Significance, and Scientific Rationale:**

It is established that impulsivity is a tremendous risk factor for the development of addiction (Bickel et al., 2007) and for treatment failure (Loree, Lundahl, & Ledgerwood, 2015). Impulsivity is a multi-faceted trait that has been conceptually divided into a more decision-based domain and rapid “acting without thinking” motoric domain(Swann, [name], Moeller, & Dougherty, 2002), where greater impulsivity in both domains has been found in patients addicted to stimulants in particular (Ahn & Vassileva, 2016). Trait personality measures of impulsivity typically capture some elements of both domains and frequently correlate poorly with individual task metrics of impulsivity. Therefore, comprehensive assessment of cognitive change (as it may underlie improvements in mental perseverance and thus changes in substance use) should include objective behavioral measures of both decision-making and motoric impulsivity. The addition of focused neurocognitive tasks holds potential to *identify mechanisms of* psychotherapy effects, such as whether a structured cognitive behavioral therapy may reduce substance use by promoting mindful attention generally, or whether it influences future-orientation specifically.

There are currently multiple treatments being conducted in the IOP clinic as standard of care, with a particular psychotherapy of interest for this study being a brief, structured cognitive-based treatment, called the Mind Freedom Plan (MFP). This treatment is one of two treatments being administered, with the other being a supportive, unstructured treatment that is also provided as standard of care. The aim of the MFP treatment is to improve problem solving abilities, increase engagement in pleasurable activities, and teach the patient to identify and change maladaptive thoughts. Structured worksheets for each session have been developed for

the purpose of achieving these goals. An exploratory aim of the current study will be to identify whether there are neurobehavioral differences in subjects as a result of the treatment modality being conducted during their treatment regimen. This is novel due to the lack of studies previously examining neurobehavioral impulsivity tasks as a metric for exploring differences in treatment modality.

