#### Subject groups (inclusion and exclusion criteria):

##### *Inclusion criteria:*

- Enrollment in the Substance Abuse Treatment Program – Intensive Outpatient Program
- Currently meets criteria for an Alcohol or Substance Use Disorder per SUD clinic intake

*Exclusion criteria:*

- Unable to read and speak English
- Currently active-duty military
- Current engaged with legal involvement that is mandating the completion of the substance use program.

Collection of written informed consent:

The capacity to provide informed consent may be impaired in some patients, and we will not enroll decisionally-impaired individuals. Therefore, we will pay special attention to mental capacity and ability to provide informed consent. The determination of such capacity rests in a few key items:

- The subject should be able to understand the general procedures of the experiment and what is expected of him/her during participation.
- The subject should be able to understand the risks and benefits associated with the study.
- The subject should be able to understand that he/she can decline the study or withdraw from the study at any time after entering the study.

We will confirm that all participants understand the informed consent process by asking them to summarize the key points in their own words. The consent form will convey that confidentiality is limited in situations where the subject is assessed to be a threat in harming self or others. Subjects will be provided with a written copy of the consent form. The research staff will point out the contact numbers listed on the consent form for the PI [name] (for questions, comments, or concerns). Finally, as a safety precaution, each subject will be provided with a VA suicide hotline information card.

**8. Consultants:** none

**9. Curriculum Vitae:** Principal Investigator's CV is on file with other projects, but can be provided if requested.

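### The covariates named to handle confounding leave out baseline substance use and substance class, so both are left free to confound the impulsivity–outcome association

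*Protocol*

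**What the plan says.** The last sentence of the Data Analysis section gives the covariates and their purpose: "Individual differences in PTSD and anxiety measures and other symptomatology will be included as covariates to account for confounding factors in the analyses". The outcomes listed above it include "proportion drug-free urines" and retention in the program, to be compared by t-test or chi-square.

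Aim 1 asks whether neurobehavioral function "is predictive of treatment success and adherence outcomes", with urine and breath results, no-shows, drop-out and recidivism as examples.

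Other places bear on the choice of covariates:

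- **Inclusion criteria:** "Currently meets criteria for an Alcohol or Substance Use Disorder per SUD clinic intake". No criterion restricts substance type or recent use, and nothing stratifies by them.
- **Background:** greater impulsivity is reported by substance, "where greater impulsivity in both domains has been found in patients addicted to stimulants in particular".
- **Visit One, BAM:** the instrument "assesses the recent occurrence and frequency of various substances, including marijuana, cocaine, stimulants, and opiates", and the protocol adds: "We hypothesize subjects with more reported substance use and less engagement in treatment resources will have poorer treatment adherence".
- **Visit One, PTSD checklist and anxiety inventory:** each has the same stated role, "This measure is being used to account for potential confounding symptomology that may lead to treatment adherence issues". The BAM has no such role and does not appear in the Data Analysis section.

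**The concern.** The protocol does not leave adjustment open for later. It names a set of variables and says they are there to deal with confounding. That set omits a baseline measure the protocol itself expects to predict adherence, and a patient characteristic it links to impulsivity.

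In a sample mixing alcohol-only and drug-using Veterans, an association between task scores and drug-test results could partly reflect which substance each Veteran uses, or how much he or she used before entry. It could then be reported as impulsivity carrying information about treatment failure beyond those facts.

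Precision is a second, separate loss. A baseline measure of use is the natural covariate for a substance-use outcome, and it matters for the MFP versus TAU comparison even though that comparison is not threatened by confounding in the same way.

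**Working it through.** **1. Which links the protocol states**

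| Factor | Link to impulsivity | Link to outcome |
|---|---|---|
| Substance class | Stated for stimulant addiction (Background) | Not stated |
| Baseline use | Not stated | Hypothesized, for adherence (Visit One, BAM) |

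Confounding needs both links for the same factor. The protocol supplies one for each, so the supportable statement is that both factors are left free to confound.

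**2. Stated figures**

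The protocol gives about 35 Veterans and no alpha, power, effect size or SD. There is no figure to reproduce. What follows is illustration with assumed inputs.

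**3. One omitted confounder, n = 35, no true association**

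Assume the confounder correlates r with both the task score and the outcome. The spurious correlation is then r × r. At two-sided 0.05 the critical correlation is t/√(t² + 33) with t = 2.03, which gives 0.334. False-positive rates come from 40,000 simulated data sets per row.

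| Assumed r | Spurious correlation r² | False positives, unadjusted | False positives, adjusted |
|---|---|---|---|
| 0.2 | 0.04 | 5.5% | 5.1% |
| 0.3 | 0.09 | 8.1% | 5.1% |
| 0.4 | 0.16 | 14.8% | 5.0% |
| 0.5 | 0.25 | 30.7% | 4.9% |
| 0.6 | 0.36 | 58.1% | 5.0% |

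**4. Substance class as the confounder**

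Assumptions: half the sample alcohol-only and half drug users; 8 urines each; impulsivity d SD higher in drug users; positive-urine rates p₁ (drug) and p₀ (alcohol-only); beta-binomial urines with concentration 2; no association within class.

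- Class with score: (d/2)/√(1 + d²/4).
- Within-class outcome variance: mean of p(1 − p), times 1/8 + (7/8)(1/3) = 0.417.
- Class with outcome: ((p₁ − p₀)/2)/√(within-class variance + ((p₁ − p₀)/2)²).
- Spurious correlation ρ: the product of the two.

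| d | p₁ vs p₀ | Class–score | Class–outcome | ρ | False positives |
|---|---|---|---|---|---|
| 0.3 | 30% vs 10% | 0.148 | 0.371 | 0.055 | about 6% |
| 0.5 | 40% vs 10% | 0.243 | 0.497 | 0.12 | about 10% |
| 0.8 | 50% vs 5% | 0.371 | 0.671 | 0.25 | about 30% |

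The middle row in full: 0.25/√1.0625 = 0.243. The within-class variance is ((0.24 + 0.09)/2) × 0.417 = 0.0688, so 0.15/√(0.0688 + 0.0225) = 0.497. The product is 0.12.

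The last column uses Fisher's z, with standard error 1/√32 = 0.177 and atanh(0.334) = 0.347. For ρ = 0.12 the upper tail is (0.347 − 0.121)/0.177 = 1.28, or 10.0%. The lower tail adds 0.4%.

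**5. Precision**

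If baseline use correlates r with the drug-test outcome, adjustment lowers the residual variance by r²: 4% at r = 0.2, 9% at 0.3, 25% at 0.5. In a two-group comparison one covariate takes 1 of 35 − 2 = 33 residual degrees of freedom, about 3%. The gain is roughly nil at r = 0.2 and worthwhile from moderate correlations upward.

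**The case against.** - **The list is open-ended.** Its closing symptom term could take in BAM items on craving, and detailed covariate lists often go to an analysis plan that is not shown. This stands in part. Craving may count as a symptom, but the amount of use and the type of substance do not naturally do so. The protocol also chose to state the set and its purpose.
- **Aim 1 is about prediction.** A marker may predict an outcome even if part of the association runs through substance type. This stands. The unadjusted association answers the aim as worded, so it should be kept; adjustment answers the further question of what the tasks add.
- **Adjusting for use may remove real signal.** The Background treats impulsivity as a risk factor for developing addiction, so prior use may lie on its path to poor outcome. This stands, and is the reason for reporting both estimates.
- **The sizes are invented.** They are assumed, and at the low end the bias is negligible. The rates of 30% and above need strong links that the documents do not support.
- **Few covariates fit in about 35 Veterans.** True, and it argues for one use score and one binary indicator, not a longer list.
- **The covariate sentence follows the MFP versus TAU comparison.** It nonetheless refers to the analyses in general. If it did not reach Aim 1, that aim would have no stated adjustment.

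A reader might infer more than the text allows: that the protocol shows class and prior use to be linked to both impulsivity and outcome, so that the Aim 1 result is confounded. It states one link for each. A reader might also infer that recent use goes unrecorded. The BAM records it; only eligibility leaves it unrestricted.

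**Conclusion.** The concern holds in a limited form. The stated covariate set omits baseline substance use and substance class, although the protocol expects the first to predict adherence and ties stimulant addiction to impulsivity. In a sample open to any alcohol or substance use disorder, both are left free to confound the Aim 1 association. The protocol does not establish that they do.

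The size is not given. Under the assumed class scenarios the spurious correlation is about 0.05 to 0.25, with false-positive rates of about 6% to 30% against a nominal 5% at n = 35. These rest on an even class split, 8 urines per Veteran, and assumed shifts and rates. Weak links make the problem negligible; moderate to strong ones make it serious.

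The loss of precision from omitting baseline use depends on its correlation with the drug-test outcome, also not given. The change is worth making because it is cheap and uses data already at hand, not because a large bias has been shown.

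**What to change.** Amend the Data Analysis section as follows:

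1. Keep the PTSD, anxiety and symptom covariates, and name depression among the symptoms so that it is not lost.
2. Add two covariates: recent use on the Visit One BAM, and a binary substance class (alcohol only versus any drug) from the clinic intake diagnosis already read for eligibility.
3. Use linear or logistic regression for the drug-test and retention analyses, including MFP versus TAU, because the listed t-tests and chi-square tests cannot carry covariates.
4. For Aim 1, report the association without and with the two added covariates. The first shows overall prediction; the second shows prediction beyond substance class and prior use.

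The cost is wording, one field from the chart, and one or two degrees of freedom in about 35 Veterans. Nothing further is asked of participants. The adjusted Aim 1 estimate may remove some of impulsivity's effect that acts through use, and the report should say so.
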